## **9.6.2 Missed Doses**

### **9.6.2.1 Morning Dose of Study Drug**

If a subject misses the morning dose of study drug (TC or placebo) and recalls within 6 hours, the subject should take his/her dose with food. If more than 6 hours but fewer than 12 hours have elapsed after his/her usual dosing time, the subject should take the morning dose of TC or placebo but skip the evening dose of study drug (IVA or placebo). If more than 12 hours have elapsed after his/her usual dosing time, the subject should skip the morning dose of TC or placebo and take the evening dose of IVA or placebo.

### **9.6.2.2 Evening Dose of Study Drug**

If a subject misses the evening dose of IVA or placebo and recalls within 6 hours, the subject should take his/her dose with food. If more than 6 hours have elapsed after his/her usual dosing time, the subject should skip that dose and resume his/her normal schedule for the following dose.

## **9.7 Dose Modification for Toxicity**

No dose modifications for toxicity are allowed. Treatment may be interrupted as outlined in Section 9.8. If any unacceptable toxicity arises, individual subjects will discontinue dosing ([Section 9.1.4](#)).

## **9.8 Study Drug Interruption and Stopping Rules**

The medical monitor should be notified of an interruption of study drug that lasts >72 hours for any reason and of the resumption of study drug after such interruption.

### **9.8.1 Liver Function Tests**

The central laboratory will notify the medical monitor of ALT or AST  $>3 \times$  ULN and total bilirubin  $>2 \times$  ULN that are derived from centrally submitted samples.

Subjects with new treatment-emergent ALT or AST elevations of  $>3 \times$  ULN, with or without total bilirubin  $>2 \times$  ULN, must be followed closely, including confirmatory testing performed by the central laboratory within 48 to 72 hours of the initial finding and subsequent close monitoring of ALT, AST, and bilirubin levels, as clinically indicated.

If a subject cannot return to the site for confirmatory testing, a local laboratory may be used. Local laboratory results must be reported immediately to the medical monitor, and the subject must have the tests repeated and sent to the central laboratory as soon as possible (ideally within 48 to 72 hours).

Study drug administration **must be interrupted** immediately (prior to confirmatory testing) if any of the following criteria are met:

- ALT or AST  $>8 \times$  ULN
- ALT or AST  $>5 \times$  ULN for more than 2 weeks
- ALT or AST  $>3 \times$  ULN, in association with total bilirubin  $>2 \times$  ULN and/or clinical jaundice

A thorough investigation of potential causes should be conducted, and the subject should be followed closely for clinical progression.

Study drug administration **must be discontinued** if the following criterion is met:

- Subsequent ALT or AST values confirm the initial elevation that satisfied the interruption rule (above), and no convincing alternative etiology (e.g., acetaminophen use, viral hepatitis, alcohol ingestion) is identified, regardless of whether transaminase levels have improved

All subjects in whom treatment is discontinued for elevated transaminases (and bilirubin, as applicable) should have these levels monitored closely until levels normalize or return to baseline.

If an alternative, reversible cause of transaminase elevation with or without increased bilirubin or clinical jaundice has been identified, study drug administration may be resumed once transaminases return to baseline or are  $\leq 2 \times$  ULN, whichever is higher. Regardless of the duration of interruption, the medical monitor should be notified prior to resumption of study drug. Upon resumption of study drug, transaminases and bilirubin should be assessed weekly for 4 weeks. If a protocol-defined transaminase elevation interruption threshold recurs within 4 weeks of rechallenge with the study drug (with confirmation of the initial elevation by repeat testing within 48 to 72 hours), then the study drug must be permanently discontinued, regardless of the presumed etiology.

### **9.8.2 Rash**

Individuals who develop a generalized rash will be monitored closely. Study drug dosing should be interrupted if a subject develops a generalized rash of Grade 3 or higher, or a rash that is considered a serious adverse event. The investigator will notify the medical monitor of any rash that results in interruption of study drug, is Grade 3 or higher ([Section 13.1.1.4](#)), or is a serious adverse event (SAE). Investigators should consider additional evaluation including laboratory testing (e.g., complete blood count [CBC] with differential, LFTs), photographs of the rash, and dermatology consultation. The investigator may consider resumption of study drug if considered clinically appropriate.

### **9.9 Removal of Subjects**

Subjects may withdraw from the study at any time at their own request. Subjects may be withdrawn from study drug treatment at any time at the discretion of the investigator or Vertex for safety, behavior, noncompliance with study procedures, or administrative reasons. If a subject has been withdrawn from study drug treatment, the subject will continue to be followed, provided that the subject has not withdrawn consent (and assent, as applicable).

In addition, a subject must be discontinued from study drug treatment if the subject meets any of the following criteria:

- Has a screening *CFTR* genotype that does not confirm study eligibility if a previous *CFTR* genotype laboratory report was used to establish eligibility. These subjects must be discontinued from the study ([Section 8.1](#))
- Meets any of the stopping (discontinuation) criteria ([Section 9.7](#))
- Becomes pregnant ([Section 11.7.7.2](#))

Subjects who discontinue study drug treatment should return for study assessments, as noted in [Section 9.1.4](#).

If a subject does not return for a scheduled visit, reasonable effort will be made to contact the subject. In any circumstance, reasonable effort will be made to document subject outcome. The investigator will inquire about the reason for withdrawal, request that the subject return all unused investigational product(s), request that the subject return for an ETT Visit and Safety Follow-up Visit, if applicable (see [Section 9.1.4](#)), and follow up with the subject regarding any unresolved AEs.

If the subject withdraws consent or assent for the study, no further assessments will be performed. Vertex may retain and continue using the study data and samples after the study is over, and may use the samples and information in the development of the study compound, and for other drugs and diagnostics, in publications and presentations, and for education purposes. If the subject withdraws from the study, the study data and samples collected will remain part of the study. A subject will not be able to request the withdrawal of his/her information from the study data. A subject may request destruction of the samples collected from him/her during the study as long as those samples can be identified as his/her samples.

#### **9.10 Replacement of Subjects**

Subjects who withdraw or are withdrawn before the first dose of study drug on Day 1 may be replaced.

Subjects who withdraw or are withdrawn for nonsafety reasons during the study drug Treatment Period may be replaced at Vertex's discretion.

### **10 STUDY DRUG INFORMATION AND MANAGEMENT**

Study drug refers to VX-659/TEZ/IVA, IVA, and their matching placebos.

#### **10.1 Preparation and Dispensing**

Study drug may be dispensed only under the supervision of the investigator or an authorized designee and only for administration to the study subjects.

#### **10.2 Packaging and Labeling**

Study drug tablets will be supplied in blister cards by Vertex. Study drug labeling will be in compliance with applicable local and national regulations. Additional details regarding packaging, labeling, and dispensing for study drug will be in the Pharmacy Manual.

#### **10.3 Study Drug Supply, Storage, and Handling**

VX-659/TEZ/IVA will be supplied as 2 FDC film-coated tablets (120 mg VX-659/50 mg TEZ/75 mg IVA). Matching VX-659/TEZ/IVA placebo tablets will be of similar size and appearance and contain 0-mg VX-659, 0-mg TEZ, and 0-mg IVA ([Table 10-1](#)).

IVA (150 mg) will be supplied as tablets containing 150-mg IVA. Matching IVA placebo tablets will be of similar size and appearance and contain 0-mg IVA ([Table 10-1](#)).

Blister cards must be stored under conditions noted in the Pharmacy Manual. The investigator, or an authorized designee (e.g., a licensed pharmacist), will ensure that all investigational product is stored in a secured area, under recommended storage conditions, and in accordance with

applicable regulatory requirements. To ensure adequate records, all study drugs will be accounted for via the drug accountability forms as instructed by Vertex.

**Table 10-1 Study Drug: Strength/Dosing Form/Route**

Drug Name, Dosing Form, Route	Strength
VX-659/TEZ/IVA, FDC tablet, oral	
VX-659	120 mg
TEZ	50 mg
IVA	75 mg
VX-659/TEZ/IVA-matching placebo, tablet, oral	0 mg
IVA, tablet, oral	150 mg
IVA-matching placebo, tablet, oral	0 mg

FDC: fixed-dose combination; IVA: ivacaftor; TEZ: tezacaftor

#### **10.4 Drug Accountability**

The pharmacist or designated study site staff will maintain information regarding the dates and amounts of (1) study drug received; (2) study drug dispensed to the subjects; and (3) study drug returned by the subjects. Subjects will be instructed to return all used and unused materials associated with the study drug to the site. These materials will be retained at the site according to instructions provided by Vertex or its designee. The study monitor will review study drug records and inventory throughout the study.

If a site uses a site-specific drug accountability system and/or process, including processes associated with the destruction of returned materials, the process must be documented and approved by Vertex. The study monitor must review the drug accountability documentation on a regular basis. The study monitor will promptly communicate to Vertex any discrepancies he/she is unable to resolve with the site.

#### **10.5 Disposal, Return, or Retention of Unused Drug**

The study site staff or pharmacy personnel will retain all materials returned by the subjects until the study monitor has performed drug accountability. The investigator will ensure that the materials are destroyed in compliance with applicable environmental regulations, institutional policy, and any special instructions provided by Vertex. Destruction will be adequately documented.

#### **10.6 Compliance**

To ensure treatment compliance, the investigator or designee will supervise all study drug dosing that occurs at the site. At each visit, site personnel will review that the subject is compliant with study drug dosing and remind the subject of study drug dosing requirements. Compliance will also be assessed by ongoing study drug count.

If a subject demonstrates continued noncompliance of study drug dosing despite educational efforts, the investigator should consider discontinuing the subject from the study.

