### 9.1.2 Treatment Period

The Treatment Period will be randomized, double-blind, and placebo-controlled. It will last approximately 24 weeks (Day 1 through Week 24). Study drug administration details are provided in [Section 9.6](#).

Randomization will occur before the first dose of study drug during the Treatment Period and may occur on either Day 1 or Day -1. Randomization and stratification details are provided in [Section 9.2](#).

Subjects who prematurely discontinue study drug treatment will remain in the study from the time of discontinuation of study drug treatment through the last scheduled study visit and complete the assessments for all study visits, as described in Section 9.1.4.

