### **9.1.4 Early Termination of Treatment**

If a subject prematurely discontinues study drug treatment, an Early Termination of Treatment (ETT) Visit should be scheduled as soon as possible after the decision to discontinue treatment. Subjects who prematurely discontinue treatment will also be required to complete the Safety Follow-up Visit, approximately 28 days after their last dose of study drug. The assessments performed at the Safety Follow-up Visit are listed in [Table 3-2](#).

If the ETT Visit occurs 3 weeks or later following the last dose of study drug, then the ETT Visit will replace the Safety Follow-up Visit, and a separate Safety Follow-up Visit will not be required.

Subjects who prematurely discontinue study drug treatment will continue to complete all scheduled study visits for assessments following completion of the ETT Visit, as detailed in [Table 3-2](#). Data regarding concomitant antibiotic therapy for sinopulmonary signs/symptoms will also continue to be collected for these subjects.

If a subject withdraws from the study and also withdraws consent or assent, no further assessments will be performed. Vertex may retain and continue to use any data and samples collected before such withdrawal of consent or assent.

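### Protocol Section 10.6 points investigators toward removing persistently noncompliant subjects from the study, which conflicts with the continued follow-up in Sections 9.1.2, 9.1.4 and 9.9

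*Protocol*

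**What the plan says.** Protocol Section 10.6 (Compliance) states that, when dosing noncompliance continues in spite of education, "the investigator should consider discontinuing the subject from the study". It does not refer the reader to Section 9.1.4 or 9.9.

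Three other sections of the protocol separate stopping drug from leaving the study:

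- Section 9.9 (Removal of Subjects) allows subjects to be "withdrawn from study drug treatment at any time at the discretion of the investigator or Vertex for safety, behavior, noncompliance with study procedures", or for administrative reasons. It adds that "the subject will continue to be followed, provided that the subject has not withdrawn consent" or, where applicable, assent.
- Section 9.1.2 (Treatment Period): "Subjects who prematurely discontinue study drug treatment will remain in the study" through the last scheduled visit.
- Section 9.1.4 (Early Termination of Treatment): "Subjects who prematurely discontinue study drug treatment will continue to complete all scheduled study visits for assessments following completion of the ETT Visit". Data on antibiotics for sinopulmonary symptoms also continue to be collected.

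Section 9.1.6 defines when participation is complete. Its categories are subjects who complete treatment (with or without entering an open-label study), subjects who stop drug early but keep consent in place, subjects who withdraw consent or assent, and subjects lost to follow-up. None describes a subject whom the investigator removes from the study for noncompliance while consent stands.

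**The concern.** Two sites could handle the same subject differently. One that follows Section 10.6 literally would take the subject out of the study and stop visits. One that follows Sections 9.1.4 and 9.9 would, if drug is stopped, keep the subject in scheduled visits to Week 24.

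Noncompliance arises after randomization and may reflect tolerability or perceived benefit, either of which can differ by arm. If such subjects leave, outcomes that could have been observed become missing. The MMRM in SAP Section 9.3.1.2 assumes they are missing at random and does not impute them. For PEx, SAP Section 9.3.2.1 ends the analysis period of a subject without a Week 24 Visit at the earlier of Day 169 and the end of participation, so removal shortens follow-up. PEx is the endpoint that set the sample size (Protocol Section 12.1). It is also second in the testing hierarchy, so a failure there blocks the five key secondary endpoints below it.

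**Working it through.** **1. The texts side by side**

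| Section | Trigger | Subject leaves | Follow-up |
|---|---|---|---|
| 10.6 | continued dosing noncompliance | the study (investigator to consider) | not stated |
| 9.9 | safety, behavior, noncompliance with study procedures, administrative reasons | study drug | continues unless consent or assent is withdrawn |
| 9.1.2, 9.1.4 | any premature stop of study drug | study drug | all scheduled visits |

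The triggers in 10.6 and 9.9 are worded differently: dosing in one, study procedures in the other. The conflict does not depend on treating them as the same. Section 9.9 also covers behavior and administrative reasons, and Sections 9.1.2 and 9.1.4 retain a subject who stops drug for any reason.

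The protocol also uses the two kinds of removal distinctly. For a screening genotype that does not confirm eligibility, Section 9.9 requires drug to stop and then says separately that the subject leaves the study. Disposition tables count the two separately (Protocol Section 12.3.2.1, SAP Section 9.2.1).

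**2. The plan's own PEx power**

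Inputs from Protocol Section 12.1: 180 per arm, 10% dropout, placebo rate 0.6 over 24 weeks, 40% reduction (so 0.36 on active), dispersion 0.5, two-sided alpha 0.05, stated power about 80%.

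For a Wald test on the log rate ratio, a subject with expected count m contributes information m/(1 + 0.5m).

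- Placebo, full follow-up: 0.6/1.30 = 0.4615
- Active, full follow-up: 0.36/1.18 = 0.3051
- n = 180 × 0.90 = 162 per arm, giving information 74.77 and 49.42
- SE = √(1/74.77 + 1/49.42) = 0.1833
- Power = Φ(0.5108/0.1833 − 1.96) = Φ(0.827) = 79.6%

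This reproduces the stated figure.

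**3. Illustration of extra removals**

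The documents give no removal rate. Extra losses of 2%, 5% and 10% of the 180 per arm, on top of the planned 10%, are assumptions. Two cases bracket the effect. In one, removed subjects contribute nothing. In the other, they leave at mid-treatment with half the expected count: placebo 0.30/1.15 = 0.2609, active 0.18/1.09 = 0.1651.

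Worked case, 5% extra (9 per arm, 153 left with full follow-up), removal at mid-treatment:

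- Placebo: 153 × 0.4615 + 9 × 0.2609 = 72.96
- Active: 153 × 0.3051 + 9 × 0.1651 = 48.16
- SE = √(1/72.96 + 1/48.16) = 0.1857
- Power = Φ(0.5108/0.1857 − 1.96) = 78.6%

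| Extra loss | Fully followed per arm | Power, removed at mid-treatment | Power, contributing nothing |
|---|---|---|---|
| 0% | 162 | 79.6% | 79.6% |
| 2% | 158.4 | 79.2% | 78.7% |
| 5% | 153 | 78.6% | 77.3% |
| 10% | 144 | 77.5% | 74.8% |

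**4. ppFEV1 power at the final analysis**

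Difference 5.0, SD 7, alpha 0.01, normal approximation: power = Φ(5/(7√(2/n)) − 2.576).

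- n = 162: Φ(6.43 − 2.58), above 99.9%
- n = 144: Φ(6.06 − 2.58), above 99.9%

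The extra removals do not matter for ppFEV1 power.

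**The case against.** The strongest reply is that this is one loosely worded phrase. Section 10.6 only asks the investigator to consider removal, and only after repeated noncompliance and education. It nowhere says that assessments stop; Sections 9.1.4 and 9.9 say that only where consent or assent is withdrawn. Section 9.1.6 can be read as keeping such a subject in follow-up, since someone off drug with consent in place completes at the latest of the Week 24, ETT or Safety Follow-up Visit. Section 13.1.1.2 also pairs a dose change with discontinuation from the study, which suggests that the term is sometimes used loosely. Sites and subjects are blinded, and the planned 10% dropout may already include these removals.

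Much of this stands. It makes the harm a possibility of unknown frequency and keeps the power effect small. It does not remove the conflict: a site cannot tell from Section 10.6 that visits should continue, and the protocol elsewhere gives removal from the study its own meaning.

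A reader might infer more than the documents support:

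- **That Section 9.9 limits noncompliance to withdrawal from drug only.** It is permissive, refers to study procedures, and never says that noncompliance cannot lead to removal from the study.
- **That the protocol follows every treated subject.** Genotype-ineligible subjects are removed from the study by design.
- **That Section 10.6 will create treatment-related missing data.** The documents give no removal rate and no evidence of a link to treatment.
- **That no sensitivity analysis covers departures from missing at random.** Parts of the SAP next to the primary analysis are redacted, so this cannot be judged.

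**Conclusion.** The conflict is real and in current text, and its severity is low to moderate. Section 10.6 points toward leaving the study where Sections 9.1.2, 9.1.4 and 9.9 keep subjects who stop drug under follow-up, and Section 9.1.6 has no completion category that fits a literal reading of 10.6.

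The main issue is possible selective loss of Week 24 and PEx outcomes. Its direction and size cannot be estimated from the documents. The power cost is minor: about 1 point for PEx at an assumed 5% extra removal at mid-treatment, and just over 2 points if those subjects contribute nothing. Both figures assume that the removals come on top of the planned 10% dropout and fall equally on the arms. The Week 4 primary endpoint is little exposed, because repeated noncompliance after education takes time to accumulate.

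**What to change.** Reconcile Section 10.6 with Sections 9.1.2, 9.1.4 and 9.9 so that dosing noncompliance alone does not end outcome collection. Decisions about study drug would stay under Section 9.9. Scheduled visits and the collection of PEx and antibiotic data would continue through Week 24 unless consent or assent is withdrawn. A cross-reference from 10.6 to 9.1.4 and 9.9 would make this plain to sites. With that wording, the existing Section 9.1.6 category for subjects who stop drug without withdrawing consent applies, and no new category is needed.

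This proposes no dosing or stopping rule. The cost is a few words, taken through the modification process in Section 13.2.3. The visits concerned are already in the schedule of assessments.

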#### **10.7 Blinding and Unblinding**

This will be a double-blind study.

### 10.7.1 Blinding

All subjects (and their parents/caregivers/companions), site personnel (including the investigator, the site monitor, and the study team), and members of the Vertex study team will be blinded to the treatment codes.

Individuals who may be unblinded include only the following:

- Any site personnel for whom this information is important to ensure the safety of the subject in the event of a life-threatening medical emergency
- Any site personnel for whom this information is important to ensure the safety of the subject and her fetus in the event of a pregnancy
- Vertex Global Patient Safety (GPS) and Regulatory Affairs personnel to satisfy serious adverse event (SAE) processing and reporting regulations
- Vendor preparing the final (production) randomization list
- Vertex IWRS Manager
- Vertex Clinical Supply Chain
- IDMC
- External independent biostatistician preparing the unblinded analysis for review by the IDMC
- Bioanalytical contract research organization (CRO) analyzing PK samples and the Vertex Bioanalytical personnel who is not a member of the study team but reviews raw data from the Bioanalytical CRO. The Vertex Bioanalytical study team member will continue to be blinded.
- Vendor for modeling and simulations performing population PK modeling in preparation for regulatory submission(s)

For the purpose of regulatory submissions, a limited Vertex team may be unblinded to the IA if the IDMC declares that the study has crossed the efficacy boundary ([Section 12.3.6.1](#)). Members of the limited Vertex unblinded team will not be involved in or influence the conduct of the remaining part of the study to protect the integrity of the study.

#### Access to Spirometry and SwCl Results:

During the conduct of the study, the Vertex study team will not have access to the spirometry or SwCl results after the morning dose on Day 1.

Shortly before any planned efficacy analysis is conducted, the spirometry and SwCl data will be reviewed for data cleaning purposes by a biostatistician who does not have access to the treatment codes.

Individual SwCl test results will not be disclosed to the study sites with the exception of the screening values. Subjects and their parents/caregivers/companions should not be informed of study-related spirometry results until Vertex has determined that the study has completed (i.e., clinical study report [CSR] finalization), regardless of whether the subject has prematurely discontinued treatment.

